## **10.5. Recording Adverse Events**

All adverse events (regardless of seriousness or relationship to study drug) including those from the time informed consent is obtained through to the final study visit are to be recorded in the eCRF. Each individual adverse event is to be listed as a separate entry. The Investigator will provide information about dates of onset and resolution, seriousness, severity, action(s) taken, outcome, and relationship to the study drug. All adverse events should be documented in the patient's source documents.

[figure not shown]
## **10.6. Reporting Adverse Events**

The Investigator must report to Sponsor or its designee all adverse events that occur during the study from the time written informed consent is given until the final study visit or early termination, regardless of their relationship to the study drug. Serious adverse events and pregnancies will be reported from the time written informed consent is given through 30 days beyond the last dose of study drug.

### **10.6.1. Reporting Serious Adverse Events**

The Investigator is required to notify the Sponsor, and the Sponsor's designated Drug Safety Unit, immediately, without undue delay, and no later than 24 hours after becoming aware of the

occurrence of a serious adverse event. All serious adverse events will be reported through completion of the adverse event eCRF. The Investigator will be responsible for reporting serious adverse events to the EC.

If an Investigator becomes aware of a serious adverse event within 30 days after the last dose of study drug and it is considered by him/her to be caused by the study drug with a reasonable possibility, the event must be documented and reported through completion of the adverse event eCRF.

#### **10.6.2. Reporting Urgent Safety Issues**

If the study site staff becomes aware of an actual or potential urgent safety issue, then the Sponsor and Sponsor's designee (Medical Monitor) must be immediately contacted so that appropriate urgent safety measures can be agreed upon. An urgent safety issue is defined as:

- An immediate hazard to the health or safety of patients participating in a clinical study
- A serious risk to human health or potentially a serious risk to human health

An urgent safety issue may include: (1) issues with an investigational drug or comparators; (2) study procedures; (3) inter-current illness (including pandemic infections); (4) concomitant medications; (5) concurrent medical conditions; or (6) any other issues related to the safe conduct of the study or that pose a risk to study patients.

In exceptional circumstances of imminent hazard and in order to safeguard the health or safety of individuals, the Investigators may take urgent safety measures before informing the Sponsor, but the Sponsor must be informed immediately after the hazard has resolved.

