### **12.3. Investigator's Responsibilities**

Investigator responsibilities are set out in the ICH Guideline for GCP and in the local regulations. Each Investigator participating in this study is required to maintain complete and accurate study documentation in compliance with current GCP standards and all applicable local regulations related to the conduct of a clinical study.

The Principal Investigator will ensure that all persons assisting with the study are adequately informed about the protocol, any amendments to the protocol, the study drug, and their study-related duties and functions. The Principal Investigator will maintain a list of sub-Investigators and other appropriately qualified persons to whom he or she has delegated significant study-related duties.

The Investigator is responsible for keeping a record of all patients who sign an informed consent document and are screened for entry into the study. Patients who fail eligibility requirements must have the reason(s) recorded in the patient's source documents.

The Sponsor, or designee, should inform the EC of any event likely to affect the safety of patients or the continued conduct of the study, in particular any change in safety. Additionally, all updates to the Investigator's Brochure will be sent to the EC. A progress report will be sent to the EC and the protocol will be reviewed annually (e.g., re-approved) or more frequently, as required by the EC or local regulations.

The Investigator will maintain a copy of all correspondence with the EC, including copies of approved documents submitted by the Sponsor or designee. The Investigator will also maintain a copy of the EC membership list with occupation and qualification (or a statement confirming compliance with GCP requirements for committee composition).

The Sponsor or designee is responsible for notifying the EC/RA of the conclusion of the clinical study within 90 days of completion of the study, per the EU Directive. In cases where a study is

terminated early, notification must be made within 15 days of the early termination. The final study report must be submitted within 1 year after study completion.

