## **12.4. Protocol Amendments**

Any permanent change to the protocol, whether it is an overall change or a change for specific study center(s), must be handled as a protocol amendment. All amendments to the protocol will be written by the Sponsor. The Investigator will not make any changes to this protocol without prior written consent from the Sponsor and subsequent approval by the EC. Except for administrative amendments, Investigators must await EC approval of protocol amendments before implementing the change(s). The Sponsor will ensure submission of any protocol amendments to the appropriate regulatory agencies and EC.

Trial conduct may be impacted in light of the COVID-19 pandemic. Challenges may arise (e.g., quarantines, site closures, travel limitations, interruptions to the supply chain for the investigational product, etc.) leading to difficulties in meeting protocol-specified procedures, including administering or using the investigational product or adhering to protocol-mandated visits and laboratory/diagnostic testing. Taking into consideration recent Regulatory Agency guidance, amendments to protocol defined criteria may be implemented without EC approval or before filing an amendment to the IND/CTA in order to minimize or eliminate immediate hazards or to protect the life and well-being of research participants (e.g., to limit exposure to COVID-19).

Administrative amendments are defined as having no effect on the safety of the research subjects, scope of the investigation, or quality of the study. However, a protocol change intended to eliminate an apparent immediate hazard to patients should be implemented immediately, and the EC notified within 5 days or per local regulations.

When, in the judgement of the chairman of the local EC, the Investigators, and/or the Sponsor, the amendment to the protocol substantially alters the study design and/or increases the potential risk to the patient, the currently approved written ICF will require similar modification. In such cases, repeat informed consent will be obtained from patients enrolled in the study before continued participation under the new amendment.

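### In the imminent-hazard exception of Protocol 10.6.2, notice to the sponsor runs from the end of the hazard, not from the site's action, so the permitted delay has no limit

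*Protocol*

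**What the plan says.** Protocol 10.6.2 has a general rule and an exception.

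- **General rule.** When site staff learn of an actual or potential urgent safety issue, the sponsor and its designee, the Medical Monitor, "must be immediately contacted so that appropriate urgent safety measures can be agreed upon". The section's list of possible issues includes the investigational drug, study procedures and intercurrent illness, pandemic infections among them.
- **Exception.** It is limited to exceptional cases of imminent hazard. In those cases "the Investigators may take urgent safety measures before informing the Sponsor". The duty that then applies is that "the Sponsor must be informed immediately after the hazard has resolved". No maximum number of hours or days is given.

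Four other sections bear on the timing.

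- Protocol 10.6.1: serious adverse events are notified "immediately, without undue delay, and no later than 24 hours after becoming aware of" the event.
- Protocol 12.2: the sponsor or its designee must see that all participating investigators are informed of significant new risk information.
- Protocol 12.3: "The Sponsor, or designee, should inform the EC of any event likely to affect the safety of patients".
- Protocol 12.4: a change to the protocol that is meant to remove an immediate hazard, it says, "should be implemented immediately, and the EC notified within 5 days or per local regulations".

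**The concern.** The trigger is attached to the wrong event. Under the general rule, even a potential issue goes to the sponsor at once. Under the exception, a site facing an imminent hazard, and sure enough of it to have acted, may wait until the hazard is over. The more urgent case therefore has the looser reporting rule.

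This matters when the hazard is not confined to one site. The SAP (8.1.1) expects about 50 sites, and Protocol 7.4.1 sets no prospective stopping criteria, so action across the study depends on what the sponsor knows. If one site has acted on a suspect batch or a faulty procedure, the others learn of it through the sponsor. That other sites might be warned late is an inference from these roles; no section says so.

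**Working it through.** No sample size, power or other statistical figure is involved, and the plan gives no figure to reproduce. The check compares the clocks.

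**Set-up.** Measure time in days from the site becoming aware of the hazard (time 0). Let *m* be the time at which the site takes its measure and *r* the time at which the hazard resolves, with *r* ≥ *m* ≥ 0. The documents give neither *m* nor *r*.

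| Rule | Sponsor must know by | Upper limit |
|---|---|---|
| 10.6.2, general rule | time 0 (immediately) | immediate |
| 10.6.2, exception | *r* | none |
| 10.6.1, if the event is a serious adverse event | 24 hours = 1 day | 1 day |
| Section 12, if it is a serious breach | time 0 (immediately) | immediate |

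**Step 1: size of the delay.** Under the exception the permitted delay from awareness is *r* − 0 = *r*, the full course of the hazard. The part not explained by the need to act first is *r* − *m*. If the measure itself ends the hazard, *r* = *m* and the excess is zero. If the hazard persists after the measure, the excess is positive and nothing in 10.6.2 limits it.

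**Step 2: what the other routes catch.**

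- Serious adverse events: 24 hours (10.6.1).
- Serious breaches of good clinical practice or the protocol: immediately on awareness (section 12).
- Pregnancy: 24 hours (10.4).
- Significant laboratory abnormalities that are serious or unexpected: promptly (9.2).
- Dose interruptions: to be discussed with the Medical Monitor (8.1), with no time limit.

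A drug-supply or procedural hazard found before harm, which is not a serious breach and has produced no reportable event, meets none of the timed routes.

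**Step 3: comparison with 12.4.** Suppose the hazard leads to a protocol change made at time *m*. Assume that the 5 days run from implementation and that the sponsor gives the notice, the role 12.3 assigns it for safety events in general. Section 12.4 states neither point. The ethics committee notice is then due at *m* + 5, and the exception requires the sponsor to know by *r*.

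- If *r* ≤ *m* + 5, the sponsor must be told no later than the day the notice is due.
- If *r* > *m* + 5, the notice falls due before the sponsor has to be told.

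The conflict thus arises only when the hazard outlasts the measure by more than 5 days and local regulations set no different period.

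**Step 4: the same clocks after the change.** If the duty runs from the measure, the sponsor must know at *m* and the excess *r* − *m* disappears. With the optional limit of 1 day from awareness, the notice is due no earlier than 0 + 5 = 5 days, which leaves at least 5 − 1 = 4 days to prepare it.

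**The case against.** The best defence is that the exception only changes the order of events: act, then tell. It covers imminent hazard to individuals. On a natural reading the measure ends that hazard, so the sponsor hears directly afterwards. If a wider problem remains, it is still an actual or potential urgent safety issue, and the general rule applies again. This reading is reasonable and may be what was meant. The sentence does not say it, however, and a site in an emergency should not have to work out which clock governs.

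A reader might also infer stronger points that the documents do not support.

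- **That 10.6.2 contradicts itself.** It does not. The sentence is an express exception, limited to exceptional circumstances. The fault lies in its trigger.
- **That the 5-day notice in 12.4 cannot be met.** That sentence concerns a protocol change, allows local regulations to set the period, and names neither the notifier nor the start of the clock. The same section has the sponsor write all amendments and requires its written consent before an investigator changes the protocol. Investigators also have their own contact with the committee, since 10.6.1 has them report serious adverse events to it. Only the conditional conflict stands.
- **That a hazard without a serious adverse event has no other route.** Several routes exist, as listed in the working. They narrow the gap without closing it.
- **That the thrombosis episode shows the clause failing.** Protocol 6.1 describes an urgent safety measure that followed reports of thrombosis and discussions with the regulator. Nothing suggests that a site acted alone under this exception or reported late. The episode shows only that urgent measures do occur in this study.

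**Conclusion.** The point holds as a defect in a reporting rule. For an imminent hazard on which a site has already acted, the literal text allows notice to the sponsor to wait for as long as the hazard lasts, with no maximum. The exposed case is narrow: a hazard that persists after the site's own measure and is neither a serious adverse event, a serious breach nor otherwise reportable on a fixed clock. Within that case the delay is unbounded, against immediate contact under the general rule of the same section.

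The clash with the ethics committee notice is secondary. It rests on four conditions: a resulting protocol change, a hazard lasting more than 5 days beyond it, a clock that starts at implementation, and the sponsor as notifier.

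No endpoint, analysis population or estimate is affected. The reason to act is patient safety at other sites, and the remedy is small.

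**What to change.** In the last sentence of Protocol 10.6.2, replace the trigger so that the sponsor must be informed *immediately after the urgent safety measure has been taken*. The investigator's freedom to act before informing the sponsor stays as it is, and no clinical rule changes.

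An outer limit could be added, for example 24 hours after the site becomes aware of the hazard. That figure is borrowed from serious adverse event reporting in 10.6.1. It is a sensible option, but the documents do not require it here.

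While the text is open, it would help to state in 12.4 who notifies the ethics committee and from what point the 5 days run.

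The cost is one clause in the next amendment (a second if 12.4 is clarified), with the usual submission to ethics committees and regulators under 12.4. It adds no visits, assessments or analyses.

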## **11. STATISTICAL METHODS**

This section describes the rules, conventions, statistical analysis, and presentation of data for this study. Full details will be provided in the statistical analysis plan (SAP) for this study.

Revisions during the study may be made to accommodate protocol amendments and to make changes to adapt to unexpected issues in study execution that could affect planned analyses. A formal SAP for the analysis and presentation of data from this study will be prepared and issued before database lock. The SAP will provide a more technical and detailed description of the proposed data analysis methods and procedures. Deviations from the statistical analyses outlined in this protocol will be included in this plan; any further modifications will be noted in the clinical study report (CSR). All statistical analyses will be performed under oversight of the Sponsor.

All available data will be included in data listings and tabulations.

All data collected in this study will be presented using summary tables and patient data listings. Summary statistics for raw and change from Baseline data of continuous variables will minimally include n, mean, standard deviation (SD), minimum, median, and maximum. For categorical variables, frequencies and percentages will be presented. Graphical displays will be provided as appropriate.

Endpoints will be assessed using simple descriptive statistics.

### **11.1. Endpoints**

#### **11.1.1. Safety**

Safety of CTP-543 will be assessed by evaluating adverse event, clinical laboratories, physical examinations, vital signs, concomitant medications, and electrocardiogram results.

#### **11.1.2. Efficacy**

Efficacy of CTP-543 will include all patients who receive study drug and have at least 1 post-treatment SALT assessment in this study. Relative change in SALT score over time will be summarized descriptively by visit, as appropriate.

### **11.2. Analyses**

Efficacy will include all patients who receive study drug and have at least 1 post-treatment SALT assessment in this study. Safety will include all patients who receive study drug. Patients will be summarized according to study drug regimen received (i.e., as treated).

Data will be summarized by dosing regimen. All data for analysis will be listed by patient. Dosing regimens for summarization will be defined in SAP.

Continuous measures will be summarized descriptively (mean, standard deviation, median, minimum value, and maximum value) and categorical measures will be presented as number and percentage.

#### **11.2.1. Disposition and Baseline Characteristics**

Disposition will be summarized by dosing regimen. The number and percentage of patients, who are enrolled, treated, prematurely discontinued, and completers will be summarized.

Baseline characteristics will be summarized by dosing regimen for patients participating in the Treatment Period. Dosing regimens for summarization will be defined in SAP.

Medical history will be coded with the Medical Dictionary for Regulatory Activities (MedDRA) terminology. Concomitant medications will be summarized by World Health Organization Drug Dictionary Anatomical-Therapeutic-Chemical classification and preferred term.

### **11.2.2. Study Drug Exposure**

For each patient, the number of days of exposure to CTP-543 will be summed across the Treatment Period. The total number of days on study drug will exclude dose interruptions. The total number of days of exposure to CTP-543 by dose will be summarized with the mean, standard deviation, median, minimum, and maximum number of days.

### **11.2.3. Safety**

All safety summaries will be descriptive with no statistical hypothesis testing and based on the Safety Population. All safety endpoints will be listed in by-patient data listings.

Adverse events will be coded using MedDRA and summarized by system organ class and preferred term. Clinically significant deteriorations in physical examination findings will be reported and summarized as adverse events.

Laboratory values will be converted to the project-defined unit of measurement, as applicable, before analysis. Abnormal, clinically significant laboratory values will be reported and summarized as adverse events.

#### **11.2.3.1. Adverse Events**

Treatment-emergent adverse events (TEAEs) will be defined as any adverse event that occurs after administration of the first dose of study drug until completion of the study or the Early Termination Visit. The number and percentage of patients who report TEAEs will be summarized by system organ class and preferred term.

Treatment emergent adverse events will also be summarized by intensity as well as relationship to study drug.

Patients who report the same preferred term on multiple occasions will be counted once for the preferred term: under the highest severity when summarized by severity and under the closest relationship to study drug when summarized by relationship. If a patient reports multiple preferred terms for a system organ class, the patient will be counted only once for that system organ class.

The number and percentage of patients who experience TEAEs will be summarized by dosing regimen for the following:

- By system organ class and preferred term
- By severity/intensity, system organ class, and preferred term
- By relationship to study drug, system organ class, and preferred term
- Serious adverse events by system organ class and preferred term
- Serious adverse events by relationship to study drug, system organ class, and preferred term

- Adverse events resulting in discontinuation of study drug by system organ class and preferred term
- Adverse events that result in study drug dose interruption by system organ class and preferred term

By-patient listings will be provided for any deaths, serious adverse events, and adverse events leading to discontinuation of treatment.

